Demographics, health status, health literacy, and diabetes knowledge	X			
Hemoglobin A1c	X		X	X
Diabetes self-management behaviors	X	X	X	X
Systolic and diastolic blood pressure	X		X	
LDL-cholesterol	X		X	
Body mass index	X		X	
Diabetes-related healthcare utilization	X		X	X
Diabetes self-efficacy, outcome expectations, and social support	X	X	X	X
Story identification and transportation	X			
Intervention follow-up exposure		X	X	X

Study Coordinator Training and Quality Assurance

The Mayo Clinic project coordinator will work with site investigators and study coordinators to oversee training of bilingual study staff at each site. We have previously described our experience training study teams for intervention delivery among Hispanic populations⁶⁷. The project coordinator will monitor quality control of the data through review of participant forms and procedures every three months. Moreover, the study statistician will perform monthly data checks (i.e., missing data, outliers).

Treatment Fidelity

Because this work will be conducted in clinical settings, it is important to evaluate barriers and facilitators to implementation across the two primary care sites¹²³. We will evaluate subset domains of the intervention delivery construct as outlined by the recently reported NIH-sponsored framework for enhancing the value of research for dissemination and implementation¹²⁴.

In the design and conduct of this study, we have incorporated recommendations from the Treatment Fidelity Workgroup¹²⁵. An intervention guide and checklist will be developed by the study team for each intervention and control component. Likewise, a checklist will be derived for collection of follow-up measures. Site principal investigators will randomly select and attend 5% of the patient visits. Based on these observations, bi-weekly meetings will be held with the study staff at each site (via videoconference) to reinforce treatment fidelity, provide corrective feedback, and to conduct additional training if needed.

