racial/ethnic minority populations, which showed a similar hemoglobin A1c reduction of 0.31 standard deviations¹²⁸. While these effects sizes are smaller than that of our pilot study, we have picked the more conservative (lower) estimate of effect size to ensure ample sample size. Hence, we can expect an effect likely to be between 0.25 and 0.31 standard deviation for the type of intervention proposed. Required sample sizes for an independent samples t-test to detect these two effect sizes, assuming 80% power, a two-tailed alternative and a 5% Type I error rate, are 252 and 145 patients per group, respectively. With 200 patients per group, we will have 80% power to detect an effect size of 0.28 standard deviations via the independent samples t-test. Accounting for approximately 12% loss to follow-up, we intend to recruit 225 patients in each group, for a total sample size of 450 participants.

Data analysis plan

Aim #1: Evaluate the efficacy of a community-derived digital storytelling intervention among Hispanic adults with poorly controlled T2D.

The primary analysis will be an independent samples t-test between the group average hemoglobin A1c values at 3 months. A two-sided alternative with a 5% type I error rate will be employed.

Supplementary analysis for the primary endpoint. Repeated measures modeling of the individual time point A1c values (including chart abstracted values at approximately 6 months) will allow for a more detailed investigation to the timing of the impact of the intervention by including all time points (including baseline). Profile analysis (Srivastava) will further assess for difference in overall means, time point, and treatment by time interactions. Covariates indicated above including demographics and clinical covariates will be included in the repeated measures and profile analysis models to assess the sensitivity of the primary analysis conditional on these potential concomitant (mediating) influences.

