Secondary analyses. The analyses applied to the primary endpoint will also be applied to each of the secondary endpoints. The subscales from the SDSCA (general diet, diabetes diet, physical activity, diabetes medication use, blood glucose monitoring) and the physical measurements (blood pressure, LDL-cholesterol, BMI) will be compared between groups using t-tests and repeated measures monitoring similar to the primary endpoint. As we have a *single variable* primary endpoint defined, there will be no adjustment for comparison-wise Type I error rate. Additional analyses will be performed to identify potential effect modifiers for the primary and secondary outcomes, i.e., sex, age, socioeconomic position, acculturation, health literacy, and diabetes knowledge.

Aim #2: Explore the effect of the digital storytelling intervention on proposed theory-based mediators of change.

We will examine the correlational structure of the covariates and their impact on the intervention effect size via repeated measures models. We will include procedures suggested by MacKinnon^{129,130} to assess mediation, fitting three general estimating equation models to the data. We will first estimate the intervention effect separately for the dependent variable (with regression adjustment for covariates); that model provides an estimate of the total effect of the intervention. Next, we will estimate the intervention effect for each mediator (with regression adjustment for covariates); that model provides an estimate of the effect of the intervention on the mediator. Finally, we will estimate the mediated intervention effect for the dependent variable by adjusting for the mediator (and covariates); that model provides an estimate of the unmediated (i.e., direct) intervention effect, and the intervention-adjusted effect of the mediator on the dependent variable. These analyses will be done for the primary endpoint and each of the secondary endpoints to identify any mediators of the study results.

Table 3. Study Timeline

Tasks to be completed	Year 1	Year 2	Year 3	Year 4
Recruitment, enrollment, and baseline measures				
Intervention				
Follow-up measurements				
Data analysis				
Dissemination and sustainability plan				

Dissemination and Sustainability Plan

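### Aim #2 mediation models leave their covariates undefined and do not name the baseline mediator or baseline outcome, so the mediator-to-outcome path can be biased

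*Combined protocol and SAP*

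**What the plan says.** The Data analysis plan for Aim #2 proposes "fitting three general estimating equation models to the data". The first gives the total effect of arm on the outcome, the second the effect of arm on each mediator. The third is introduced as follows: "Finally, we will estimate the mediated intervention effect for the dependent variable by adjusting for the mediator (and covariates". The text then says that this third model yields the direct effect and the arm-adjusted effect of the mediator on the outcome. All three adjust for covariates, with no list given for Aim #2. The exercise is to be run for the primary endpoint and every secondary endpoint.

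The nearest description of the covariates is in the Aim #1 supplementary analysis: "Covariates indicated above including demographics and clinical covariates will be included in the repeated measures and profile analysis models". The Design Overview uses the same word more loosely, for measures tied to the theoretical framework. Baseline A1c has one stated modelling role, as a repeated time point in the Aim #1 supplementary model.

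In Table 2 the row "Diabetes self-efficacy, outcome expectations, and social support" is marked at baseline, 6 weeks, 3 months and 6 months. A1c, self-management behaviours, blood pressure, LDL-cholesterol and body mass index also have baseline values. Story identification and transportation are marked once only.

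**The concern.** Randomisation makes the arm-to-mediator comparison fair. It does nothing for the mediator-to-outcome comparison. A participant who arrives with higher self-efficacy and a lower A1c than others will tend to have both at follow-up, whatever the video does. Unless the third model holds the starting values fixed, its mediator coefficient contains that pre-existing association. Multiply it by a genuine arm effect on the mediator and the result is a non-zero indirect effect, even if changing the mediator does nothing to the outcome.

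Hypothesis 2 is a formal hypothesis about mediation, and Specific Aim #2 uses the result to build a conceptual framework of mechanisms. A wrong answer would credit self-efficacy, outcome expectancy or social support with an effect on diabetes outcomes that it does not have.

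**Working it through.** **Inputs from the documents.** The plan gives no figure for Aim #2, so the analysable sample size is the only anchor: "With 200 patients per group, we will have 80% power to detect an effect size of 0.28 standard deviations via the independent samples t-test". This reproduces: 0.28 × √(200/2) = 2.80, and Φ(2.80 − 1.96) = Φ(0.84) ≈ 0.80. The recruitment target less loss to follow-up is similar: 450 × 0.88 = 396.

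**Assumed inputs, not in the documents.**
- r, the baseline correlation between mediator and outcome: -0.1, -0.2, -0.3.
- rm and ry, the correlation of mediator and outcome with their own baselines (tracking): both 0.5 or both 0.7.
- a, the arm effect on the mediator: 0, 0.25 and 0.31 SD. The last two are borrowed from the plan's range for A1c ("we can expect an effect likely to be between 0.25 and 0.31 standard deviation for the type of intervention proposed") and are not an estimate for any mediator.
- The true effect of mediator on outcome is zero, and no other covariates are fitted.

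**Model.** M1 = rm·M0 + a·T + error, and Y1 = ry·Y0 + error, with corr(M0, Y0) = r and T the arm. Without baselines, the expected mediator coefficient is b = r × rm × ry and the false indirect effect is a × b. For r = -0.3 and tracking 0.7, b = -0.3 × 0.7 × 0.7 = -0.147.

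**Hand check of that cell.** The standard error of b is about 1/√400 = 0.05, so z = 2.94 and power is Φ(2.94 − 1.96) ≈ 0.84. For a = 0.31 the standard error is √(2/200) = 0.10, so power is Φ(3.1 − 1.96) ≈ 0.87. The product is about 0.73.

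**Simulation.** There were 200 per arm and 1,500 trials per setting, with single-time-point regressions. Entries are the percentage of trials in which both paths are significant at 5%.

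| r | tracking | expected b | no baselines, a = 0 | no baselines, a = 0.25 | no baselines, a = 0.31 | both baselines, a = 0.25 / 0.31 |
|---|---|---|---|---|---|---|
| -0.1 | 0.5 | -0.025 | 0.3 | 6.5 | 5.9 | 3.7 / 4.5 |
| -0.1 | 0.7 | -0.049 | 0.9 | 12.3 | 16.0 | 4.9 / 5.3 |
| -0.2 | 0.5 | -0.050 | 1.1 | 12.3 | 14.3 | 4.2 / 5.0 |
| -0.2 | 0.7 | -0.098 | 2.2 | 32.7 | 42.9 | 4.5 / 4.9 |
| -0.3 | 0.5 | -0.075 | 1.3 | 22.1 | 28.3 | 3.1 / 4.5 |
| -0.3 | 0.7 | -0.147 | 4.5 | 58.4 | 74.9 | 4.6 / 4.5 |

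A separate run with 396 analysed, a = 0.35, r of -0.2 to -0.3, rm of 0.5 to 0.6 and ry of 0.6 to 0.7 gave 21% to 67% without baselines and 4% to 5% with both.

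Two further results matter. With a = 0 the average indirect effect is zero, yet the mediator coefficient on its own is still falsely significant in 7.8% to 84.1% of trials. The plan states no rule for calling a construct a mediator, so which quantity is read as evidence makes a difference. In absolute terms the false indirect effect is small: at a = 0.31 it is at most 0.31 × 0.147 ≈ 0.046 SD.

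**The case against.** The strongest reply is that the plan is silent on baseline values rather than opposed to them. A reader might infer that the models exclude the baselines. The text does not support that: the Aim #1 wording introduces demographic and clinical covariates as examples rather than a closed list, and baseline A1c could count as clinical. The covariate set is undefined. This part of the reply stands, but it does not remove the point, because an analyst following the text would have no instruction to include either baseline.

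A reader might also infer that false mediation is bound to be reported. It is not. The arm-to-mediator path is estimated as its own step and is protected by randomisation. Without an arm effect on the mediator, joint false positives stay at or below about 5%.

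The simulated analysis is also simpler than the planned one. It uses one visit and no covariates, whereas the plan has estimating equations with adjustment, and health literacy, diabetes knowledge, acculturation and socioeconomic measures are collected. These could absorb part of the association. Entry restricted to A1c of at least 8% may weaken the baseline correlation for A1c, though it does not directly restrict self-management behaviours. For behaviours, the Theoretical approach section itself cites an association with self-efficacy and social support.

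A further tempting reading is that baseline rows enter the mediation models and make the bias worse. Only the Aim #1 A1c model is said to include baseline as a time point; the Aim #2 text does not say which visits enter, so this is conjecture.

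Finally, the three models do supply every component of an indirect effect, and a published mediation procedure is cited. The promise of a mediated effect from a model then said to give the direct effect is loose wording rather than a wrong method. Still, no step in the document turns the components into an estimate with an interval.

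**Conclusion.** The point holds as an unspecified adjustment that leaves a non-randomised path open to bias. It does not show that the planned analysis must give a false answer. Two conditions are needed together: the intervention moves the mediator, and a mediator-outcome correlation from before randomisation persists to follow-up. The plan hypothesises the first. The size of the second is not documented.

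Over the assumed range, false joint significance runs from roughly 6%, close to nominal, to 75%, and returns to about 5% with both baselines. The width of that range reflects how little the documents say about the correlations, and the criterion that both paths be significant is an assumption too.

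Aim #2 is exploratory and the primary t-test is unaffected. The change is nonetheless worth making before analysis, because the baseline values are already scheduled.

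**What to change.** In the Aim #2 section:

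1. List the covariates. For self-efficacy, outcome expectancy and social support, include the pre-randomisation mediator and the pre-randomisation value of the outcome in both the mediator model and the mediator-to-outcome model. The total-effect model compares randomised arms and does not need the baseline mediator for validity.
2. Name the post-baseline visits at which mediator and outcome are taken.
3. Report the indirect effect with a confidence interval by a stated method, and correct the sentence that equates the third model with the mediated effect. The choice of interval method is the sponsor's.
4. State that story identification and transportation, measured once, cannot be adjusted for a baseline value of the mediator, and that confounding of mediator and outcome by other or later factors may remain for all constructs.

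In the simulation either baseline alone removed the bias, because the only link ran from baseline mediator through baseline outcome. Naming both also covers a direct effect of the baseline mediator on the later outcome, or of the baseline outcome on the later mediator.

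The cost is SAP wording and two degrees of freedom per model. No new data, visits or participants are needed.
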